8.1.5 Best Response at an Interim Analysis using irRECIST

Similar to assigning best response by RECIST v1.1 at an interim analysis, if a subject has an unconfirmed response (i.e., one visit assessment of CR or PR) by irRC or irRECIST as the last disease assessment before an interim analysis, the best response in the interim analysis will be reported as an unconfirmed CR (uCR or uirCR) or unconfirmed PR (uPR or uirPR).

8.2 Exploratory Endpoints

Exploratory endpoint analyses, except for analysis of patient reported outcome (PRO) quality of life using the EORTC QLQ-C30 results, are outside the scope of this Statistical Analysis Plan.

8.3 Baseline, Worst, and Best-case Post-Baseline Values

Unless otherwise noted, baseline is defined as the last non-missing value recorded before the first dose of study drug. Unscheduled visits will be used in the determination of baseline values, when applicable.

Worst-case post-baseline values will be identified from all scheduled and unscheduled visits. For measures with degradation from both increases and decreases, Worst-cases will be identified and summarized for both.

Best-case post-baseline values will be identified from all scheduled and unscheduled visits. For measurable tumor assessment Best-case will be identified as the largest decrease, or, for subjects who have no decrease, the smallest increase in post-baseline assessment.

8.4 Missing Data

Subjects who discontinue from the study before completing an on-study radiographic tumor evaluation will be counted as non-responders in the evaluation of ORR.

Subjects who discontinue from the study or who are lost to follow-up without objective tumor progression while on treatment will be censored on the date of the last assessment documenting absence of disease progression in the evaluation of PFS and DoR. Subjects who discontinue from the study or who are lost to follow-up before death will be censored at the date they were last known to be alive in the evaluation of OS.

The following algorithms will be applied to missing and incomplete start and stop dates (i.e., AEs and concomitant medications):

Start Dates

- If the day portion of the start date is missing, then the start date will be estimated to be equal to the date of first dose of study drug, provided the start month and year are the same as the first dose of study drug and the stop date is either after the first dose of study drug or completely missing. Otherwise, the missing day portion will be estimated as '01'.
- If both the day and month portions of the start date are missing, then the start date will be estimated to be equal to the date of first dose of study drug, provided the start year is the same as the first dose of study drug and the stop date is either after the first dose of study drug or completely missing. Otherwise, the event will be assumed to start on the first day of the given year (e.g., ??-??-2013 is estimated as 01-JAN-2013).
- If the start date is completely missing and the stop date is either after the dose of study drug or completely missing, the start date will be estimated to be the date of first dosing of the study drug. Otherwise, the start date will be estimated to be the first day of the same year as the stop date. All other non-AE and non-concomitant medication day calculations where only partial dates are available will be handled as follows: the first day of the month will be used in the calculations if the day part of a start date is missing and January 1 will be employed if both the month and day parts of a start date are missing.

Stop Dates

- If only the end day is unknown, the day will be assumed to be the last day of the month (e.g., ??-JAN-2013 will be treated as 31-JAN-2013).
- If both the end day and month are unknown, the event will be assumed to have ceased on the last day of the year (e.g., ??-??-2013 will be treated as 31-DEC-2013).
- If the stop date is completely missing or the event is continuing, the event will be assumed to be after first dose of study drug and will be imputed using the last known date on the study.

No imputations will be made for missing values other than those described in this section. Summaries will be based on observed data only.

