3.2.2 Study Duration and Study Completion

The study ends approximately 1 year after the last subject in Phase 2 has commenced study treatment. Subjects who complete or discontinue study treatment prior to progression will be followed for clinical and radiological evidence of progression and immunogenicity assessment at least every 3 months until documentation of RECIST v1.1 progressive disease (PD), start of a subsequent anti-cancer treatment regimen, withdrawal of consent, death, or Sponsor notification that follow-up is no longer required, whichever comes first. Best response to first subsequent therapy, AEs which are Grade ≥ 3 , and concomitant medications used to treat these AEs, will also be captured during the follow-up phase of the study (Table 4 and Table 5).

After documentation of PD or use of a subsequent anti-cancer treatment regimen, all subjects will be contacted by telephone every 3 months for a survival follow-up until the site is notified by the Sponsor that survival follow-up is no longer required. A subject has completed the study at the earliest of death or study end.

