8.1 Best Overall Response

The best overall response is the best response across all disease assessment visits after baseline taking into account requirements for confirmation. For any response criteria, the best overall response for each subject will be determined by examining investigator-assessed visit-level responses and determining the best confirmed response using the assignment rules in Section 8.1.1 or Section 8.1.2, as appropriate (Paules et al, 2010). Only visit-level disease assessments prior to the start of new anti-cancer therapy or response per the appropriate criteria will be considered.

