8.5 Efficacy Endpoints

ORR is defined as the proportion subjects with a best confirmed overall response of complete response (CR) or partial response (PR), with assessment of response to be determined by the investigator using irRECIST and RECIST v1.1.

OS is defined as the number of months from initiation of treatment to death from any cause. Subjects who have not died at their last contact will be censored on the date of last contact. The specifications for the time to death calculation are:

- If death is reported either on AE or Death CRF pages, OS will be calculated as *Date of Documentation of (Death – First Dose Date + 1) / 30.4375*.
- Subjects will be censored at their last contact date if death is not reported at the data cut-off date for study closure, and their survival time will be calculated as *(/Last Contact Date - First Dose Date + 1) / 30.4375*). Last contact date is defined as the last date reported among, Adverse Event (AE start date), the Study Exit Status, Hematology, Chemistry, Assessment of RECIST v1.1 Response, Assessment of irRECIST Response, Long Term Follow Up, Study Drug Administration (IMO-2125), ipilimumab Infusion and pembrolizumab Infusion pages of the eCRF.
- Subjects lacking data after the date of first dose who do not die will have their survival time censored on the date of first dose with duration of 1 day.

PFS, defined as number of months from the initiation of treatment to disease progression using RECIST v1.1 or irRECIST or death from any cause, will be calculated as *([Date of Documentation of Death or Disease Progression – First Dose Date + 1]/30.43750*. Subjects without reported progression at their last contact date will be censored on the date of their last valid disease assessment. A valid disease assessment is any disease assessment with overall visit-level response of irCR irPR, irSD, or irPD (without subsequent confirmation) when using irRECIST and CR, PR, or SD when using RECIST v1.1. Subjects who start new anti-cancer therapy before a PFS event will be censored on the date of initiation of new anti-cancer therapy (Subsequent Anti Cancer Therapy eCRF page).

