Duration of response, defined as the length of time from the first occurrence of confirmed response (CR or PR) until confirmed (if necessary) disease progression with assessment of response to be determined by the Investigator using the irRECIST, and RECIST v1.1. DoR will be calculated as *[Date of Documentation of Death or Disease Progression – Date of First Objective Response]/30.4375*. The censoring rules for PFS will be used for DoR. Subjects who

fail to achieve a CR/irCR or PR/irPR during the study will be excluded from the analysis of DoR.

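### Section 8.4 gives a partial start date of subsequent anti-cancer therapy no lower bound, so the imputed date can fall before the progression it followed, or before first dose

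*SAP*

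**What the plan says.** SAP Section 8.4 gives separate start-date rules for adverse events and concomitant medications, then a catch-all: "All other non-AE and non-concomitant medication day calculations where only partial dates are available will be handled as follows". Under it "the first day of the month will be used in the calculations if the day part of a start date is missing". A date of which only the year is known becomes the first of January. The section closes the door on anything else: "No imputations will be made for missing values other than those described in this section".

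Subsequent anti-cancer therapy has its own eCRF page, named in Section 8.5, and nothing exempts its start date from the catch-all. That date is used in three places:

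- PFS (8.5): "Subjects who start new anti-cancer therapy before a PFS event will be censored on the date of initiation of new anti-cancer therapy".
- DoR (8.5): "The censoring rules for PFS will be used for DoR".
- Best overall response, and so the primary ORR (8.1): "Only visit-level disease assessments prior to the start of new anti-cancer therapy or response per the appropriate criteria will be considered".

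**The concern.** New therapy usually follows progression. Imputing its start to the earliest possible day therefore errs in the direction that matters: the therapy can be dated ahead of the progression, and Section 8.5 then treats the progression as unobserved. The subjects affected are ones who did progress, so the censoring is informative and pushes the PFS and DoR curves upward.

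The adverse-event and medication rules refer to the first-dose date. The catch-all refers to no date at all: not first dose, last dose, last scan or progression. A year-only date can therefore land before treatment began. That gives a PFS time that cannot exist, and under Section 8.1 it leaves no post-baseline scan eligible, so a confirmed responder would be counted as a non-responder in the primary test.

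**Working it through.** **Design figures the response count feeds (SAP Section 4).** Ipilimumab arm: continue with at least 2 of 10, reject with at least 6 of 21, null 0.11, alternative 0.35. Exact binomial calculation:

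- Early stopping under the null = P(X ≤ 1 | 10, 0.11) = 0.697.
- Expected N = 10 + (1 − 0.697) × 11 = 13.33.
- Power = sum over x ≥ 2 of P(X₁ = x | 10, 0.35) × P(X₂ ≥ 6 − x | 11, 0.35) = 0.773.

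These match the SAP's 69.7%, 13.33 and 77%. The design is not in question; it shows where one response matters.

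**How often the order is reversed.** Assumptions, since the SAP gives neither figure: progression is equally likely on each day of two calendar years (730 days), and therapy truly starts g days later. An event is lost when the imputed start falls before the progression date.

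*Day missing.* In a month of L days, this needs progression on day 2 or later and therapy still in that month, which leaves L − g − 1 days (zero if negative). Summed over 24 months and divided by 730:

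| Gap g (days) | Days affected | Share |
|---|---|---|
| 7 | 730 − 24 × 8 = 538 | 74% |
| 14 | 730 − 24 × 15 = 370 | 51% |
| 21 | 730 − 24 × 22 = 202 | 28% |
| 28 | 14 × 2 + 8 × 1 = 36 | 5% |
| 35 or more | 0 | 0% |

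(At 28 days, the 14 months of 31 days give 2 days each, the 8 of 30 days give 1, and February gives none.)

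*Day and month missing.* The same argument over a year gives (365 − g − 1)/365:

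- g = 7: 357/365 = 98%.
- g = 28: 336/365 = 92%.
- g = 42: 322/365 = 88%.
- g = 90: 274/365 = 75%.

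**PFS example.** First dose 1 March 2017, progression 20 June, therapy 27 June. PFS = (date − first dose + 1)/30.4375.

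- True: 112/30.4375 = 3.68 months, event.
- Day missing, imputed 1 June: 93/30.4375 = 3.06 months, censored.
- Year only, imputed 1 January: −58/30.4375 = −1.91 months, censored before first dose.

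**Response example.** Same first dose; PR at Week 8 (19 April), confirmed at Week 17 (21 June), progression at Week 29 (13 September), therapy recorded as 2017 only. The imputed start is 1 January 2017, no post-baseline scan is prior to it, and the confirmed PR is lost.

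**What one lost response does at the boundary** (exact one-sided binomial, the test in Section 9.2):

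- Ipilimumab arm, null 0.11: 6/21 gives p = 0.022; 5/21 gives p = 0.073.
- Pembrolizumab arm, null 0.05: 4/21 gives p = 0.019; 3/21 gives p = 0.085.

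Either conclusion at the 0.025 level would reverse.

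**The case against.** The best case for leaving the rule alone has four parts.

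*The day-missing problem may be small.* Footnotes to the schedules of evaluations (Tables 4 and 5) ask for a confirmatory scan at least 4 weeks after progression is first documented. If therapy waits for that scan, the gap is at least 28 days and the share affected is 5% or less: about 0.5% averaged over gaps of 28 to 42 days, and about 5% over 14 to 90. This stands as a limit on size. An average of 24% over gaps of 7 to 42 days can be computed, but it rests on the short gaps and should not be quoted alone. Nothing shown makes therapy wait, so short gaps remain possible.

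*For ORR the rule is conservative.* It can remove responses but cannot credit one achieved on later therapy. That is true and defensible for a single-arm test, but it does not justify discarding scans taken before any new therapy could have begun, or dating that therapy before first dose.

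*PFS and DoR are descriptive Kaplan-Meier summaries with no test.* Also true, and it limits the severity.

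*Partial dates may be rare.* A reader might infer from "all subjects will be contacted by telephone every 3 months for a survival follow-up" (Section 3.2.2) that therapy dates come from telephone calls and are often partial. The text does not say that: it describes survival follow-up, not the source of therapy dates, and contact every 3 months would tend to fix the month.

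Reading the therapy as a concomitant medication does not rescue the rule. The other bullets in Section 8.4 then give day 01, January 1 or the first-dose date, and the first-dose date also precedes every post-baseline scan.

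**Conclusion.** The rule is wrong as written and should be corrected. Followed literally, Sections 8.1, 8.4 and 8.5 together can date therapy before the progression it followed, and with year-only dates can produce negative PFS times and the loss of a confirmed response.

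The size is conditional. Among day-missing dates the share reversed runs from 74% at a 7-day gap to none from 35 days; among year-only dates it is 88% to 98% for gaps of 7 to 42 days. The gaps are assumptions, and the SAP gives no frequency of partial dates, so no overall bias in PFS, DoR or ORR can be stated.

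Two stronger readings should be resisted. One is that every partial date deletes an event: reversal needs progression and therapy in the same month (day missing) or the same year (month missing), with progression after the imputed day. The other is that the primary test is generally at risk: that mainly needs a responder who later starts new therapy, a date whose month is unknown, an unfavourable position in the calendar year, and a count at the rejection boundary.

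**What to change.** Add a rule to Section 8.4 for the start date of subsequent anti-cancer therapy:

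1. Impute a partial date as the later of the first day of the known month or year and the day after the last study-drug dose, kept within the known period and never before first dose.
2. If only the day is missing and progression by the criterion being analysed (RECIST v1.1 or irRECIST) falls in the same month, impute the day after that progression, capped at month end, so that the progression stays an event.
3. For year-only dates, query the site. If the date stays unresolved, report PFS, DoR and ORR under both the earliest and the latest admissible date.

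The day-after-progression convention should not extend to year-only dates. If therapy began in February and progression came in November, it would date the therapy to November and count scans taken on the new drug toward ORR.

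In the response example, suppose the last dose was at Week 23 (1 March + 154 days = 2 August). The earliest admissible start is then 3 August: both response scans count and the PR is kept. The 13 September progression is censored under the earliest date and is an event under the latest (31 December), which is the uncertainty the sensitivity analysis should show.

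The cost is a few lines in the SAP, a short derivation, and site queries for any year-only dates; no new visits or subjects. One small downside is that the same-month convention could count a progression as an event when therapy truly began a few days before it.

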8.5 Efficacy Endpoints

ORR is defined as the proportion subjects with a best confirmed overall response of complete response (CR) or partial response (PR), with assessment of response to be determined by the investigator using irRECIST and RECIST v1.1.

OS is defined as the number of months from initiation of treatment to death from any cause. Subjects who have not died at their last contact will be censored on the date of last contact. The specifications for the time to death calculation are:

- If death is reported either on AE or Death CRF pages, OS will be calculated as *Date of Documentation of (Death – First Dose Date + 1) / 30.4375*.
- Subjects will be censored at their last contact date if death is not reported at the data cut-off date for study closure, and their survival time will be calculated as *(/Last Contact Date - First Dose Date + 1) / 30.4375*). Last contact date is defined as the last date reported among, Adverse Event (AE start date), the Study Exit Status, Hematology, Chemistry, Assessment of RECIST v1.1 Response, Assessment of irRECIST Response, Long Term Follow Up, Study Drug Administration (IMO-2125), ipilimumab Infusion and pembrolizumab Infusion pages of the eCRF.
- Subjects lacking data after the date of first dose who do not die will have their survival time censored on the date of first dose with duration of 1 day.

PFS, defined as number of months from the initiation of treatment to disease progression using RECIST v1.1 or irRECIST or death from any cause, will be calculated as *([Date of Documentation of Death or Disease Progression – First Dose Date + 1]/30.43750*. Subjects without reported progression at their last contact date will be censored on the date of their last valid disease assessment. A valid disease assessment is any disease assessment with overall visit-level response of irCR irPR, irSD, or irPD (without subsequent confirmation) when using irRECIST and CR, PR, or SD when using RECIST v1.1. Subjects who start new anti-cancer therapy before a PFS event will be censored on the date of initiation of new anti-cancer therapy (Subsequent Anti Cancer Therapy eCRF page).

Duration of response, defined as the length of time from the first occurrence of confirmed response (CR or PR) until confirmed (if necessary) disease progression with assessment of response to be determined by the Investigator using the irRECIST, and RECIST v1.1. DoR will be calculated as *[Date of Documentation of Death or Disease Progression – Date of First Objective Response]/30.4375*. The censoring rules for PFS will be used for DoR. Subjects who

fail to achieve a CR/irCR or PR/irPR during the study will be excluded from the analysis of DoR.

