8.1.3 Confirmed Response using irRC and irRECIST

Table 7 incorporates the response confirmation rules indicated in the irRC and irRECIST guidelines (see Appendix B and Appendix D).

Table 7 Confirmed Response using irRC or irRECIST

Visit-Level Response	Next Visit-Level Response	Confirmed Response
CR	CR	CR (if visit-level disease assessments are \geq 28 days apart), otherwise SD
CR	PR	PR (if visit-level disease assessments are \geq 28 days apart), otherwise SD
CR	SD	SD
CR, PR, SD	PD	SD
CR, PR	NE	SD
PR	CR, PR	PR (if visit-level disease assessments are \geq 28 days apart); otherwise, SD
PR	SD	SD
SD	SD, CR, PR, PD, NE	SD
PD	PD	PD (if visit-level disease assessments are \geq 28 days apart), otherwise, NE .
CR, PR, SD	No 2 nd visit	SD
PD	No 2 nd visit	NE
NE	No 2 nd visit	NE

The minimum interval for confirmation of CR, PR and PD is 28 days. Subjects must have at least one post-baseline disease assessment to be assigned SD as the best overall response; otherwise, there is no minimum interval for assignment of SD as the best overall response. The same algorithm as for RECIST v1.1 criteria will be used to determine time between disease assessments for confirmation of CR, PR, and PD.

In some situations, it may be necessary to check across more than two sequential time points in order to determine whether or not a minimum duration criteria has been met. The same logic as used for the pairs of time points should be applied. For example, note the following examples.

- For the triplet CR NE CR, if the minimum criteria for CR duration is met for the interval between the two CR assessments, then **Confirmed Response = CR**. Otherwise **Confirmed Response = SD**.
- For the triplet CR CR CR, if the minimum criteria for CR duration is met for the interval between the first and third CR assessments, then **Confirmed Response = CR**. Otherwise **Confirmed Response = SD**.
- For the triplet PR NE PR, if the minimum interval criteria for PR is met for the interval between the two PR assessments, then **Confirmed Response = PR**. Otherwise **Confirmed Response = SD**.
- For the triplet PR PR PR, if the minimum interval criteria for PR is met for the interval between the first and third PR assessments, then **Confirmed Response = PR**. Otherwise **Confirmed Response = SD**.

For confirmed progression using irRC and irRECIST.

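### irRECIST PFS and DoR treat every unconfirmed irPD as a progression-free assessment, including those never rescanned, which conflicts with SAP Section 8.4 and biases irPFS upward

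*SAP*

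**What the plan says.** Section 8.5 defines the PFS event as "disease progression using RECIST v1.1 or irRECIST or death from any cause". Its censoring rule is: "Subjects without reported progression at their last contact date will be censored on the date of their last valid disease assessment". What counts as valid depends on the criteria. For RECIST v1.1 it is "CR, PR, or SD when using RECIST v1.1", so PD is excluded. For irRECIST the list has irCR, irPR and irSD, and adds "or irPD (without subsequent confirmation) when using irRECIST". On a change of treatment: "Subjects who start new anti-cancer therapy before a PFS event will be censored on the date of initiation of new anti-cancer therapy". The paragraph on duration of response in Section 8.5 adopts the PFS censoring rules.

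Section 8.4 covers subjects who leave the study or are lost without objective progression while on treatment. They "will be censored on the date of the last assessment documenting absence of disease progression in the evaluation of PFS and DoR".

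Section 8.1.3 sets the confirmation rule: "The minimum interval for confirmation of CR, PR and PD is 28 days". Table 7 in that section gives NE, not PD, to an irPD with no second visit. Appendix D also requires irPD to be confirmed.

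**The concern.** Two quite different subjects have an unconfirmed irPD. In one, a later scan shows that the irPD was not real progression. In the other, no later scan exists. Section 8.5 handles both as progression-free on the irPD date.

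For the second kind, the missing scan may itself be related to prognosis. Section 3.2.2 ends scheduled radiological follow-up off treatment at RECIST v1.1 PD or at new therapy and moves the subject to telephone contact. The confirmatory scan asked for in the footnotes to Tables 4 and 5 may therefore not happen. If those subjects have a worse outlook than the subjects who stay in the risk set, the censoring is informative.

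At stake are the irRECIST PFS curve, its median and its 6- and 12-month proportions (Section 9.3.2), and irRECIST DoR. One progressing scan that is never repeated is an event in the RECIST v1.1 PFS table and a censored observation in the irRECIST table, so part of any gap between the two tables would come from this rule.

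**Working it through.** **1. What the text does with a never-rescanned irPD**

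| What follows the irPD | Treatment under Section 8.5 | Effect on irPFS |
|---|---|---|
| No recorded death, no new therapy (lost, withdrawn, alive at cut-off) | Censored at the irPD date | Progression lost |
| New therapy | Censored at start of new therapy | Progression lost, extra event-free time credited |
| Death without new therapy | Event at death | Event kept, but late |

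Section 8.4 would send a subject who leaves after an irPD back to the last scan that showed no progression. Section 8.5 stops at the irPD scan. The two rules give different censoring dates for the same subject.

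**2. Illustration of size**

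The SAP states no PFS figure to reproduce. From the SAP come the scans at Weeks 8, 17 and 29 (Tables 4 and 5), the 6-month time point (Section 9.3.2) and the divisor 30.4375 (Section 8.5). Assumed: exponential time to progression with median 3 months; a share q of irPDs never rescanned; mean 2 months from irPD to death; new therapy 1 month after irPD; confirmed irPD dated at first documentation.

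Scan times in months: 8 × 7 / 30.4375 = 1.840 and 17 × 7 / 30.4375 = 3.910. Week 29 falls at 6.67 months, so only two scans affect the 6-month value.

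*Comparator (never-rescanned irPD is an event at first irPD).* S1 = 2^(−1.840/3) = 0.654; S2 = 2^(−3.910/3) = 0.405. So 6-month irPFS is 40.5% (40.4% in a simulation of 200,000 subjects).

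*All censored at irPD.* Kaplan-Meier at 6 months = [1 − (1 − q)(1 − S1)] × [1 − (1 − q)(1 − S2/S1)]. With q = 0.20 and S2/S1 = 0.620: 0.723 × 0.696 = 0.503 (simulation 50.2%).

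*All die and are counted at death.* S2 + q × [(1 − S1) × e^(−(6 − 1.840)/2) + (S1 − S2) × e^(−(6 − 3.910)/2)]. With q = 0.20: 0.405 + 0.20 × [0.346 × 0.125 + 0.249 × 0.352] = 0.431 (simulation 43.0%).

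*Mixed: half die, a quarter switch, a quarter are censored at irPD.* Simulation only: 46.3% at q = 0.20.

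Simulated 6-month irPFS, with the rise over 40.4% in points:

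| q | All die, counted at death | Mixed | All censored at irPD |
|---|---|---|---|
| 10% | 41.8% (+1.4) | 43.4% (+3.0) | 45.2% (+4.8) |
| 20% | 43.0% (+2.6) | 46.3% (+5.9) | 50.2% (+9.8) |
| 30% | 44.3% (+3.9) | 49.3% (+8.9) | 55.5% (+15.1) |
| 50% | 46.9% (+6.5) | 55.3% (+14.9) | 67.0% (+26.6) |

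**3. Sensitivity to the assumptions**

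Study Week 8 begins 7 weeks after first dose. With scans at 7 and 16 weeks, S1 = 0.689 and S2 = 0.427. The all-censored case at q = 0.20 is then 0.752 × 0.696 = 0.523, a rise of 9.6 points. With an assumed median of 5 months the comparator is 58.0%; at q = 30% the three cases give 61.0%, 64.9% and 69.5%, rises of 3.0, 6.9 and 11.5 points. The direction is upward in every case run.

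**The case against.** The strongest reply is that irRECIST is meant to work this way. Appendix D and Section 8.1.3 do not accept a single irPD as progression, and Table 7 calls an irPD without a second visit NE. On that view Section 8.5 simply carries the confirmation rule into PFS. This stands for an irPD that a later scan refutes: not counting it is correct, and striking unconfirmed irPD from the valid list altogether would be too blunt. It does not rescue the never-rescanned case. A scan whose confirmed status is NE does not show that progression is absent, which is what Section 8.4 asks of a censoring assessment.

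A reader might infer that subjects too ill to be rescanned drop out of the analysis as if event-free. The documents do not support that. Death from any cause is a PFS event, and Section 3.2.2 seeks deaths by telephone every 3 months after PD or new therapy. A subject who deteriorates and dies without new therapy is a late event, not a removed one. One gap remains: the sentence censoring subjects without reported progression does not expressly exempt a death after an unconfirmed irPD.

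A reader might also take the 9-to-10-point rise as the expected bias. It is the upper scenario, in which no never-rescanned subject dies or switches.

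Finally, irPFS is a descriptive secondary estimate with no test, the SAP plans no formal comparison of the two criteria, and confirmatory scans are planned. All of that is true. It limits the consequence but does not settle which of the two sections the programmer should follow.

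**Conclusion.** The point holds in this form. Section 8.5 merges refuted and never-rescanned irPD into one valid progression-free category, contradicts Section 8.4, and biases irRECIST PFS upward, with the same censoring passed on to irRECIST DoR.

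The direction is clear; the size is not fixed by the SAP, which gives no rate of unconfirmed irPD and none for death or switching after it. At an assumed 3-month median and 20% never rescanned, the rise in 6-month irPFS lies between about 3 points (all die and are counted) and 9 to 10 points (all censored at irPD), with about 6 in the mixed case. That missing confirmatory scans are linked to poor prognosis is a reasonable assumption, not something the SAP states.

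The RECIST v1.1 ORR test and RECIST v1.1 PFS do not use this rule and are unaffected. The change should be made, but the study's primary conclusion does not depend on it.

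**What to change.** - Reconcile Sections 8.4 and 8.5 so that one censoring rule applies to irRECIST PFS and DoR.
- Count an irPD with no later assessment before new therapy, death or loss as an event at the first irPD date.
- Continue follow-up past an irPD that a later scan refutes.
- State that death after an unconfirmed irPD is an event. This still matters for a subject whose irPD was refuted, and for the sensitivity analysis below.
- Keep the present censoring rule as a sensitivity analysis, and report how many subjects it treats differently.

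The cost is SAP wording and one re-run of the irRECIST PFS and DoR outputs, with no new data. The downside is that a few pseudo-progressors who are never rescanned will be counted as events; the sensitivity analysis shows how much that matters.
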